### **13.2. Independent Ethics Committee or Institutional Review Board (IEC/IRB)**

Before the start of the study, the investigator will provide the IEC/IRB with current and complete copies of the following documents:

- final protocol and, if applicable, amendments
- informed consent form (and any other written materials to be provided to the subjects)

- Investigator's Brochure (or equivalent information) and amendments
- information on compensation for study-related injuries or payment to subjects for participation in the study, if applicable
- investigator's curriculum vitae or equivalent information (unless not required, as documented by IEC/IRB)
- information regarding funding, institutional affiliations, other potential conflicts of interest, and incentives for subjects
- any other documents that the IEC/IRB requests to fulfil its obligation

If study drug is being provided, it will not be shipped until after IEC/IRB has given full approval of the final protocol, amendments (if any), the informed consent form, applicable recruiting materials, and subject compensation programs, and the Investigator-sponsor has received a copy of this approval. This approval letter must be dated and must clearly identify the documents being approved.

During the study the investigator will send the following documents to the IEC/IRB for their review and approval, where appropriate:

- protocol amendments
- revision(s) to informed consent form and any other written materials to be provided to subjects
- if applicable, new or revised subject recruiting materials approved by the sponsor
- revisions to compensation for study-related injuries or payment to subjects for participation in the study, if applicable
- Investigator's Brochure amendments or new edition(s)
- summaries of the status of the study (at least annually or at intervals stipulated in guidelines of the IEC/IRB)
- reports of adverse events that are serious, unlisted, and associated with the investigational drug
- new information that may affect adversely the safety of the subjects or the conduct of the study
- deviations from or changes to the protocol to eliminate immediate hazards to the subjects
- report of deaths of subjects under the investigator's care
- notification if a new investigator is responsible for the study at the site
- any other requirements of the IEC/IRB

For protocol amendments that increase subject risk, the amendment and applicable informed consent form revisions must be submitted promptly to the IEC/IRB for review and approval before implementation of the change(s).

At least once a year, the IEC/IRB will be informed about the clinical ongoing of this clinical study. This request should be documented in writing.

At the end of the study, the investigator (or sponsor where required) will notify the IEC/IRB about the study completion.

### 13.3. Informed Consent

Each subject (or a legally acceptable representative) must give written consent according to local requirements after the nature of the study has been fully explained. The consent form must be signed before performance of any study-related activity. The consent form that is used must be approved by IELSG and by the reviewing IEC/IRB. The informed consent should be in accordance with principles that originated in the Declaration of Helsinki, current ICH and GCP guidelines, applicable regulatory requirements, and sponsor policy.

Before entry into the study, the investigator or an authorized member of the investigational staff must explain to potential subjects or their legally acceptable representatives the aims, methods, reasonably anticipated

benefits, and potential hazards of the study, and any discomfort it may entail. Subjects will be informed that their participation is voluntary and that they may withdraw consent to participate at any time. They will be informed that choosing not to participate will not affect the care the subject will receive for the treatment of his/her disease. Subjects will be told that alternative treatments are available if they refuse to take part and that such refusal will not prejudice future treatment.

The subject or legally acceptable representative will be given sufficient time to read the informed consent form and the opportunity to ask questions. After this explanation and before entry to the study, consent should be appropriately recorded by means of either the subject's or his/her legally acceptable representative's dated signature. After having obtained the consent, a copy of the informed consent form must be given to the subject.

Subjects will also be asked to consent to participate in a genetic research component of the study. Refusal to participate will not result in ineligibility for the rest of the clinical study unless participation in genetic testing is required as an inclusion criterion. After informed consent is appropriately obtained, the subject or his/her legally acceptable representative will sign and personally date a separate DNA informed consent form indicating agreement or refusal to participate in the genetic testing. A copy of this informed consent form will be given to the subject.

If the subject or legally acceptable representative is unable to read or write, an impartial witness should be present for the entire informed consent process (which includes reading and explaining all written information) and personally date and sign the informed consent form after the oral consent of the subject or legally acceptable representative is obtained.

## 13.4. Privacy of personal data

The collection and processing of personal data from subjects enrolled in this study will be limited to those data that are necessary to investigate the efficacy, safety, quality, and utility of the investigational product(s) used in this study.

These data must be collected and processed with adequate precautions to ensure confidentiality and compliance with applicable data privacy protection laws and regulations.

The investigator-sponsor ensures that the personal data will be

- processed fairly and lawfully
- collected for specified, explicit, and legitimate purposes and not further processed in a way incompatible with these purposes
- adequate, relevant, and not excessive in relation to said purposes
- accurate and, where necessary, kept current

Explicit consent for the processing of personal data will be obtained from the participating subject (or his/her legally acceptable representative) before collection of data. Such consent should also address the transfer of the data to other entities and to other countries.

The subject has the right to request through the investigator access to his/her personal data and the right to request rectification of any data that are not correct or complete. Reasonable steps should be taken to respond to such a request, taking into consideration the nature of the request, the conditions of the study, and the applicable laws and regulations.

## **14. ADMINISTRATIVE REQUIREMENTS**

### **14.1. Data Quality Assurance**

Steps to be taken to ensure the accuracy and reliability of data include the selection of qualified investigators and appropriate study centers, review of protocol procedures with the investigator and associated personnel before the study. Written instructions will be provided for collection, preparation, and shipment of blood, plasma, and urine samples. CRF completion guidelines will be provided and reviewed with study personnel before the start of the study. The sponsor will review CRFs for accuracy and completeness during on-site monitoring visits and after their return to the sponsor; any discrepancies will be resolved with the investigator or designee, as appropriate

Investigator will permit trial-related monitoring, providing direct access to source documents/data

### **14.2. Record retention**

Once controlled for accuracy and completeness, copy of all CRFs will be kept at the IELSG coordination office, where the contained data will be transferred into an electronic study database. The results of the study will be reported in a Clinical study Report generated by the investigator-sponsor and will contain all data from all investigational sites.

### **14.3. On-site audits**

Investigator / institution will permit trial-related audits, providing direct access to source documents / data

## Performance Status scales

The following table presents the Karnofsky performance status scale.

Which of the following descriptions best describes the subject's level of performance at this time:

Eastern Cooperative Oncology Group (Zubrod-ECOG) 		KARNOFSKY SCORE	
Description	Grade	Scale	Description
Fully active, able to carry on all pre-disease activities without restriction.	0	100 90	Normal, no complaints, no evidence of disease. Able to carry on normal activity, minor symptoms or signs of disease.
Restricted in physically strenuous activity but ambulatory and able to carry out work of a light or sedentary nature (e.g. light house work, office work)	1	80 70	Normal activity with effort, some signs or symptoms of disease. Cares for self, unable to carry on normal activity or to do active work.
Ambulatory and capable of all self care but unable to carry out any work activities. Up and about more than 50% of waking hours.	2	60 50	Requires occasional assistance, but is able to care for most of his needs. Requires considerable assistance and frequent medical care.
Capable of only limited self care, confirmed to bed or chair more than 50% of waking hours.	3	40 30	Disabled, requires special care and assistance. Severely disabled, hospitalization is indicated although death is not imminent.
Completely disabled. Cannot carry on any self care. Totally confined to bed or chair.	4	20 10 0	Hospitalization necessary, very sick, active supportive treatment necessary. Moribund, fatal processes progressing rapidly. Dead

- 1 Zubrod, C.G., et al. Appraisal of Methods for the Study of Chemotherapy of Cancer in Man. *Journal of Chronic Diseases*, 11:7-33, 1960.
- 2 Oken, M.M., et al. Toxicity and response criteria of the Eastern Cooperative Oncology Group. *Am J Clin Oncol (CCT)* 5: 649-655, 1982

## ATTACHMENT 2

### WHO classification for lymphoma

#### MYELOPROLIFERATIVE NEOPLASMS

Chronic myelogenous leukaemia, BCR-ABL1 positive	9875/3
Chronic neutrophilic leukaemia	9963/3
Polycythaemia vera	9950/3
Primary myelofibrosis	9961/3
Essential thrombocythaemia	9962/3
Chronic eosinophilic leukaemia, NOS	9964/3
Mastocytosis	
Cutaneous mastocytosis	9740/1
Systemic mastocytosis	9741/3
Mast cell Leukaemia	9742/3
Mast cell sarcoma	9740/3
Extracutaneous mastocytoma	9740/1
Myeloproliferative neoplasm, unclassifiable	9975/3

#### MYELOID AND LYMPHOID NEOPLASMS WITH EOSINOPHILIA AND ABNORMALITIES OF *PDGFRA*, *PDGFRB* OR *FGFR1*

Myeloid and lymphoid neoplasms with PDGFRA rearrangement	9965/3
Myeloid neoplasms with PDGFRB rearrangement	9966/3
Myeloid and lymphoid neoplasms with FGFR1 abnormalities	9967/3

#### MYELODYSPLASTIC/MYELOPROLIFERATIVE NEOPLASMS

Chronic myelomonocytic leukaemia	9945/3
Atypical chronic myeloid leukaemia, BCR-ABL1 negative	9876/3
Juvenile myelomonocytic leukaemia	9946/3
Myelodysplastic/Myeloproliferative neoplasm, Unclassifiable	9975/3
Refractory anaemia with ring sideroblasts associated with marked thrombocytosis	9982/3

#### MYELODISPLASTIC SYNDROMES

Refractory cytopenia with unilineage dysplasia	
Refractory anaemia	9980/3
Refractory neutropenia	9991/3
Refractory thrombocytopenia	9992/3
Refractory anaemia with ring sideroblasts	9982/3
Refractory cytopenia with multilineage dysplasia	9985/3
Refractory anaemia with excess blasts	9983/3
Myelodysplastic syndrome associated with isolated del(5q)	9986/3
Myelodysplastic syndrome, unclassifiable	9989/3
Childhood myelodysplastic syndrome	
Refractory cytopenia of childhood	9985/3

#### ACUTE MYELOID LEUKAEMIA (AML) AND RELATED PRECURSOR NEOPLASMS

#### AML with recurrent genetic abnormalities

AML with t(8;21)(q22 ;q22); RUNX1-RUNX1T1	9896/3
AML with inv(16)(p13.1q22) or t(16 ;16)(p13.1 ;q22) ; CBFB-MYH11	9871/3
Acute promyelocytic leukaemia with t(15 ;17)(q22 ;q12) ; PML-RARA	9866/3
AML with t(9 ;11)(p22 ;q23) ; MLLT3-MLL	9897/3
AML with t(6 ;9)(p23 ;q34) ; DEK-NUP214	9865/3
AML with inv(3)(q21q26.2) or t(3 ;3)(q21 ;q26.2) ; RPN1-EVI1	9869/3
AML (megakaryoblastic) with t(1 ;22)(p13 ;q13) ; RMB15-MKL1	9911/3
AML with mutated NPM1	9861/3
AML with mutated CEBPA	9861/3

#### AML with myelodysplasia-rel. changes

#### Therapy-related myeloid neoplasms

Acute myeloid leukaemia, NOS	9861/3
AML with minimal differentiation	9872/3
AML without maturation	9873/3
AML with maturation	9874/3
Acute myelomonocytic leukaemia	9867/3
Acute monoblastic and monocytic leuk.	9891/3
Acute erythroid leukaemia	9840/3
Acute megakaryoblastic leukaemia	9910/3
Acute basophilic leukaemia	9870/3
Acute panmyelosis with myelofibrosis	9931/3

#### Myeloid sarcoma

Myeloid proliferations related to Down syndrome	9930/3
Transient abnormal myelopoiesis	9898/1
Myeloid leukaemia associated with Down syndrome	9898/3

#### Blastic plasmacytoid dendritic cell neoplasm

ACUTE LEUKAEMIAS OF AMBIGUOUS LINEAGE	
Acute undifferentiated leukaemia	9801/3
Mixed phenotype acute leukaemia with t(9 ;22)(q34 ;q11.2) ; BCT-ABL1	9806/3
Mixed phenotype acute leukaemia with t(v ;11q23) ; MLL rearranged	9807/3
Mixed phenotype acute leukaemia, B/myeloid, NOS	9808/3
Mixed phenotype acute leukaemia, T/myeloid, NOS	9809/3
Natural killer (NK) cell lymphoblastic Leukaemia/lymphoma	

#### PRECURSOR LYMPHOID NEOPLASMS

B lymphoblastic leukaemia/lymphoma	
B lymphoblastic leukaemia/lymphoma, NOS	9811/3

B lymphoblastic leukaemia/lymphoma with recurrent genetic abnormalities	9812/3	Large B-cell lymphoma arising in HHV8-associated multicentric Castleman dis.	9738/3
B lymphoblastic leukaemia/lymphoma with t(9 ;22)(q34 ;q11.2) ; BCR-ABL1	9813/3	Primary effusion lymphoma	9678/3
B lymphoblastic leukaemia/lymphoma with t(v ;11q23) ; MLL rearranged	9813/3	Burkitt lymphoma	9687/3
B lymphoblastic leukaemia/lymphoma with t(12 ;21)(p13 ;q22) ; TEL-AML1 ( ETV6-RUNX1 )	9814/3	B-cell lymphoma, unclassifiable, with features intermediate between diffuse large B-cell lymphoma and Burkitt lymphoma	9680/3
B lymphoblastic leukaemia/lymphoma with hyperdiploidy	9815/3	B-cell lymphoma, unclassifiable, with features intermediate between diffuse large B-cell lymphoma and classical Hodgkin lymph.	9596/3
B lymphoblastic leukaemia/lymphoma with hypodiploidy (hypodiploid ALL)	9816/3	MATURE T-CELL AND NK-CELL NEOPLASMS	
B lymphoblastic leukaemia/lymphoma with t(5 ;14)(q31 ;q32) ; IL3-IGH	9817/3	T-cell prolymphocytic leukaemia	9834/3
B lymphoblastic leukaemia/lymphoma with T(1 ;19)(q23 ;p13.3) ; E2AA-PBX1 ( TCF3-PBX1 )	9818/3	T-cell large granular lymphocytic leukaemia	9831/3
T lymphoblastic leukaemia/lymphoma	9837/3	Chronic lymphoprolifer. disorder of NK-cells	9831/3
MATURE B-CELL NEOPLASMS		Aggressive NK cell leukaemia	9948/3
Chronic lymphocytic leukaemia/ Small lymphocytic lymphoma	9823/3	Systemic EBV positive T-cell lymphoproliferative disease of childhood	9724/3
B-cell prolymphocytic leukaemia	9833/3	Hydroa vacciniforme-like lymphoma	9725/3
Splenic B-cell marginal zone lymphoma	9689/3	Adult T-cell leukaemia/lymphoma	9827/3
Hairy cell leukaemia	9940/3	Extranodal NK/T cell lymphoma, nasal type	9719/3
Splenic B-cell lymphoma/leukaemia, unclass	9591/3	Enteropathy-associated T-cell lymphoma	9717/3
Splenic diffuse red pulp small B-cell lym	9591/3	Hepatosplenic T-cell lymphoma	9716/3
Hairy cell leukaemia-variant	9591/3	Subcutaneous panniculitis-like T-cell lymphoma	9708/3
Lymphoplasmacytic lymphoma	9671/3	Mycosis fungoides	9700/3
Waldenström macroglobulinemia	9761/3	Sézary syndrome	9701/3
Heavy chain diseases	9762/3	Primary cutaneous CD30 positive T-cell lymphoproliferative disorders	9718/1
Alpha heavy chain disease	9762/3	Lymphomatoid papulosis	
Gamma heavy chain disease	9762/3	Primary cutaneous anaplastic large cell lymphoma	9718/3
Mu heavy chain disease	9762/3	Primary cutaneous gamma-delta T-cell lymphoma	9762/3
Plasma cell myeloma	9732/3	Primary cutaneous CD8 positive aggressive	
Solitary plasmacytoma of bone	9731/3	Epidermotropic cytotoxic T-cell lymph.	9709/3
Extraosseous plasmacytoma	9734/3	Primary cutaneous CD4 positive small/medium	
Extranodal marginal zone lymphoma of mucosa-associated lymphoid tissue (MALT lymphoma)	9699/3	T-cell lymphoma	9709/3
Nodal marginal zone lymphoma	9699/3	Peripheral T-cell lymphoma, NOS	9702/3
Paediatric nodal marginal zone lymph	9699/3	Angioimmunoblastic T-cell lymphoma	9705/3
Follicular lymphoma	9690/3	Anaplastic large cell lymphoma, ALK positive	9714/3
Paediatric follicular lymphoma	9690/3	Anaplastic large cell lymph., ALK negative	9702/3
Primary cutaneous follicle centre lymphoma	9597/3		
Mantle cell lymphoma	9673/3		
Diffuse large B-cell lymphoma (DLBCL), NOS	9680/3		
T-cell/histiocyte rich large B-cell lymph	9688/3		
Primary DLBCL of the CNS	9680/3		
Primary cutaneous DLBCL, leg type	9680/3		
EBV positive DLBCL of the elderly	9680/3		
DLBCL associated with chronic inflammation	9680/3		
Lymphomatoid granulomatosis	9766/1		
Primary mediastinal (thymic) large B-cell lymphoma	9679/3		
Intravascular large B-cell lymphoma	9712/3		
ALK positive large B-cell lymphoma	9737/3		
Plasmablastic lymphoma	9735/3		

HISTIOCYTIC AND DENDRITIC CELL NEOPLASMS		POST-TRANSPLANT DISORDERS (PTLD)	LYMPHOPROLIFERATIVE
Histiocytic sarcoma	9755/3	Early lesions	
Langerhans cell histiocytosis	9751/3	Plasmacytic hyperplasia	9971/1
Langerhans cell sarcoma	9756/3	Infectious mononucleosis-like PTLD	9971/1
Interdigitating dendritic cell sarcoma	9757/3	Polymorphic PTLD	9971/3
Follicular dendritic cell sarcoma	9758/3	Monomorphic PTLD (B- and T/NK-cell types)*	
Fibroblastic reticular cell tumour	9759/3	Classical Hodgkin lymphoma type PTLD*	
Indeterminate dendritic cell tumour	9757/3		
Disseminated juvenile xanthogranuloma			

---

NOS, not otherwise specified.

The italicized numbers are provisional codes for the 4th edition of ICD-O. While they are expected to be incorporated in the next ICD-O edition, they currently remain subject to changes.

The italicized histologic types are provisional entities, for which the WHO Working Group felt there was insufficient evidence to recognize as distinct diseases at this time.

\* These lesions are classified according to the leukaemia or lymphoma to which they correspond, and are assigned the respective ICD-O code.

## **ATTACHMENT 3**

### **Instructions for the preparation and handling of DEPOCYTE injections**

DepoCytē® should be stored in a refrigerator between 2° to 8°C (DO NOT FREEZE).

The principal investigator has to authorize those personnel having access to and the ability to administer the investigational medicinal product. This will be documented on a so called "authorised personnel form" provided by the monitor. Only qualified personnel who are familiar with procedures which minimize undue exposure to themselves and to the environment shall undertake, in a self-contained protective environment, the preparation, handling and safe disposal of DepoCytē®.

The vial must be at room temperature prior to performing the following procedures. Immediately prior to withdrawing a dose of DepoCytē®, the vial should be gently agitated by rolling the vial between the palms. Avoid excessive agitation (DO NOT SHAKE). No filtering, reconstitution or dilution is required prior to withdrawing drug. DepoCytē® must be used within 4 hours of withdrawal from the single-dose vial. Since DepoCytē® does not contain any preservatives, unused portions of each vial should be properly discarded. Do not mix DepoCytē® with any other medications.

Concurrent steroid administration is important for the prevention of drug-related arachnoiditis.

Therefore the patients should receive dexamethasone 4mg po (or iv) b.i.d. on the day of intrathecal injection. Steroid medication should be continued for 5 days after Depocytē® injection as standard part of the R-CHOP regimen (i.e., Prednisone 40mg/m^2 d 1-5)

## ATTACHMENT 4

### Dispensing information for Rituximab

#### DESCRIPTION

Rituximab is a mouse/human chimeric antibody. The rituximab antibody is produced by a Chinese hamster ovary transfectoma. Rituximab will be provided in 100 mg (10 mL) and 500 mg (50 mL) pharmaceutical grade vials at a concentration of 10.0 mg of protein per mL (actual concentration should be noted on the product label).

#### RECOMMENDED PREPARATION AND ADMINISTRATION

1. Refer to the clinical trial protocol for details about the dose and dose schedule.
2. Rituximab should be stored at 2-8°C. Do not freeze or store at room temperature. The product is a protein - HANDLE GENTLY AND AVOID FOAMING. The avoidance of foaming during product handling, preparation and administration is important, as foaming may lead to the de-naturing of the product proteins.
3. All transfer procedures require strict adherence to aseptic techniques, preferably in a laminar flow hood.
4. Prepare the rituximab infusion solution as follows:
  - (a) Refrigerate (2-8°C) all materials and solutions prior to use.
  - (b) Use sterile, non-pyrogenic, disposable containers, syringes, needles, stopcocks and transfer tubing, etc.
  - (c) Transfer of the rituximab from the glass vial should be made by using a suitable sterile graduated syringe and large gauge needle.
  - (d) Transfer the appropriate amount of rituximab from the graduated syringe, into a partially filled IV pack containing sterile pyrogen-free 0.9% sodium chloride solution, USP (saline solution). **The final concentration of rituximab in saline solution should be a maximum of 1 mg/ml.** Mix by inverting the bag gently. DO NOT USE A VACUUM APPARATUS to transfer the product from the syringe to the plastic bag.
  - (e) Place an IV administration into the outflow port of the bag containing the infusion solution.
  - (f) NOTE: DO NOT USE evacuated glass containers which require vented administration sets because this causes foaming as air bubbles pass through the solution.
5. The administration of rituximab will be accomplished by slow IV infusion. CAUTION: DO NOT ADMINISTER AS AN INTRAVENOUS PUSH OR BOLUS.
6. IV pumps such as the IMED 960 may be used with the rituximab infusion. DO NOT INFUSE CONCOMITANTLY with another IV solution or IV medications. Prime the line with the rituximab solution such that approximately 30 mL are delivered
7. Administration of rituximab

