#### Caution: Do not administer rituximab as an intravenous push or bolus

Rituximab will be administered intravenously in an out- or in-patient setting. Oral premedication (1000 mg of paracetamol and 50-100 mg diphenhydramine hydrochloride) needs to be administered 30-60 minutes prior to starting each infusion of rituximab. Prednisone/prednisolone as part of the chemotherapy protocol will be administered in the prescribed dose before the infusion of rituximab, preferably as oral medication. A peripheral or central intravenous (iv) line will be established. Before starting the infusion, there should be a

ready supply of epinephrine for subcutaneous injection and diphenhydramine hydrochloride for intravenous injection, and resuscitation equipment for the emergency handling of anaphylactic reactions.

The infusion will be started at an initial rate of 50 mg/hour for the first hour. During the rituximab infusion, the patient's vital signs (blood pressure, pulse, respiration and temperature) will be monitored every 15 minutes (4x) for one hour or until stable and then hourly until the infusion is discontinued. If no toxicity is seen during the first hour, the dose rate may be escalated gradually (by increments of 50 mg/hour at 30 minute intervals) to a maximum of 300 mg/hour. If the first dose of rituximab is well-tolerated, the starting flow rate for administration of the second and subsequent infusions will be 100 mg/hour and then increased gradually (by 100 mg/hour increments at 30 minute intervals) not to exceed 400 mg/hour. Patients may experience transient fever and rigors with infusion. If any of the effects below are noted, the antibody infusion should be temporarily discontinued, the patient should be observed, and when the symptoms improve, the infusion should be continued but at half the previous rate.

Dose Rate	Fever	Rigors/chills	Mucosal congestion Edema	Drop in Systolic Blood Pressure
Decrease to 1/2 If any of these Events seen:	> 38.5°C	Mild/Moderate	Mild/Moderate	> 30 mm Hg

Following the infusion the intravenous line should be kept open for medications, as needed. If there are no complications, the intravenous line may be discontinued after one hour of observation.

Dosage: 375 mg/m^2 body surface

body surface	total dose
1.4 m 	525.0 mg
1.5 m 	562.0 mg
1.6 m 	600.0 mg
1.7 m 	637.5 mg
1.8 m 	675.0 mg
1.9 m 	712.5 mg
2.0 m 	750.0 mg

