Hours	1st application mg/h *)	mg-total	further applications mg/h *)	mg-total
0 – 1	50	50	100	100
1 – 1.5	100	100	150	175
1.5 – 2	150	175	200	275
2 – 2.5	200	275	250	400
2.5 – 3	250	400	300	550
3 – 3.5	300	550	350	725
3.5 – 4	300	700	400	925
4 – 4.5	300	850		

\*) With a concentration of 1 mg/ml the values of mg/h are equal to ml/h

Suggested Rituximab Rapid infusion

If no adverse events occurred during first Rituximab infusion, with adequate premedication, II-III and IV Rituximab infusion will be performed as follows:

rituximab 375 mg/m 	First dose of 100 mg in saline solution 100 ml
	Second dose (to total dose) mg in saline solution 250 ml

time	ml/h
0-60	100
61-180	125

## ATTACHMENT 5

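### In Attachment 4, the second portion of the optional rapid rituximab infusion exceeds the protocol's own 1 mg/ml limit at every tabulated dose

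*Combined protocol and SAP*

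**What the plan says.** Section 6.1 sends sites to Attachment 4 for calculating, preparing and handling rituximab. Within that attachment:

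- Item 4(d) of the preparation instructions, in bold, states: "The final concentration of rituximab in saline solution should be a maximum of 1 mg/ml".
- The administration text starts later infusions at 100 mg/h, raises them in increments of 100 mg/h every 30 minutes, and caps them at 400 mg/h.
- The dose table applies 375 mg/m² to body surface areas of 1.4 to 2.0 m² and runs from 525 to 750 mg.
- The standard infusion table works at the limit; its footnote reads "With a concentration of 1 mg/ml the values of mg/h are equal to ml/h".
- A further block is headed "Suggested Rituximab Rapid infusion". It is conditional on a first infusion without adverse events and says "II-III and IV Rituximab infusion will be performed as follows". The preparation is "First dose of 100 mg in saline solution 100 ml", then "Second dose (to total dose) mg in saline solution 250 ml", run at 100 ml/h for minutes 0-60 and 125 ml/h for minutes 61-180.

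Nothing in the attachment exempts the rapid schedule from item 4(d).

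**The concern.** The bolded limit carries no qualification, and the rapid schedule stands in the same attachment. A site that chooses the rapid option and prepares it exactly as described produces a second portion that item 4(d) does not allow.

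The footnote to the standard table adds a risk of misreading. It equates ml/h with mg/h, which is true only at 1 mg/ml. A reader who carried it over to the rapid block directly below would take 125 ml/h for 125 mg/h, when delivery on the final-volume reading is 1.7 to 2.6 times that.

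What is at stake is a drug-preparation instruction that breaks the protocol's own rule when followed.

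**Working it through.** **Inputs, all from Attachment 4.** Limit 1 mg/ml; first portion 100 mg in 100 ml; second portion (dose − 100) mg in 250 ml; doses from the dose table; vial strength "at a concentration of 10.0 mg of protein per mL"; pump rates and times from the rapid block.

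**Reproducing the attachment's own figures.** 375 × BSA gives the dose table, except that 1.5 m² is printed as 562.0 where 375 × 1.5 = 562.5, which is immaterial here. The cumulative amounts in the standard table also reproduce, ending at 850 mg (first application) and 925 mg (further applications). The rapid pump times match the stated volumes: 1 h × 100 ml/h = 100 ml and 2 h × 125 ml/h = 250 ml. The figures are therefore unlikely to be a fault of text extraction.

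**First portion.** 100 / 100 = 1.0 mg/ml, at the limit. If the 10 ml of drug is added to 100 ml of saline, 100 / 110 = 0.91 mg/ml. It complies on both readings.

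**Second portion.** Write r = dose − 100.

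- Reading A, 250 ml is the final volume: concentration = r / 250.
- Reading B, drug at 10 mg/ml is added to 250 ml of saline: concentration = r / (250 + r/10).

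| Dose (mg) | r (mg) | A (mg/ml) | B (mg/ml) | Rate under A, × 125 ml/h (mg/h) |
|---|---|---|---|---|
| 525 | 425 | 1.70 | 1.45 | 212.5 |
| 562 | 462 | 1.85 | 1.56 | 231.0 |
| 600 | 500 | 2.00 | 1.67 | 250.0 |
| 637.5 | 537.5 | 2.15 | 1.77 | 268.75 |
| 675 | 575 | 2.30 | 1.87 | 287.5 |
| 712.5 | 612.5 | 2.45 | 1.97 | 306.25 |
| 750 | 650 | 2.60 | 2.06 | 325.0 |

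All seven rows exceed 1 mg/ml on both readings. The pump times favour reading A: under B the bag would hold 250 + 42.5 = 292.5 ml to 250 + 65 = 315 ml, and two hours at 125 ml/h would not empty it.

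**Pooling both portions.** Dose / 350 gives 1.50 to 2.14 mg/ml (1.30 to 1.76 with drug volume added), still above the limit.

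**Where the limit would be met.** Reading A: r = 250, so the dose is 350 mg and BSA = 350 / 375 = 0.93 m². Reading B: r = 250 / 0.9 = 277.8, so the dose is 377.8 mg and BSA is 1.01 m². Both lie below the table's lowest row.

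**Rate step.** Under A the rate goes from 100 ml/h × 1.0 mg/ml = 100 mg/h to 212.5-325 mg/h, a single step of 112.5 to 225 mg/h against increments of 100 mg/h in the text. Under B it goes from about 91 mg/h to about 182-258 mg/h, a step of about 91 to 167 mg/h. The lowest dose would then not exceed 100 mg/h, so the step finding depends partly on the volume reading. The concentration finding does not.

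**The case against.** The strongest reply is that the rapid schedule is only suggested. A site can satisfy item 4(d) in full by using the standard table, and Section 6.2.2 says that rituximab administration must follow the product label. The first part stands, and it limits the reach of the point. The second does not remove the conflict: the label is not among the documents, and Section 6.1 names Attachment 4 as the source for preparation, so a site that goes there meets both instructions.

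A reader might also infer more than the documents support:

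- *That the whole rapid infusion is over the limit.* The first portion is not.
- *That no pharmacy can comply.* It can, by not using the option.
- *That the fifth and sixth infusions have no instructions.* The rapid block names the second to fourth only, although six courses are planned. The standard rules for second and subsequent infusions still cover the rest. The restriction is unexplained, but it leaves no gap.
- *That the rate cap is broken.* The highest rate, 325 mg/h, is under 400 mg/h. Only the size of the step departs from the text. If the text's first increment falls at 30 minutes, its own rule reaches 100 + 2 × 100 = 300 mg/h by minute 60, so for most doses the level reached is not unusual.
- *That the primary safety results are compromised.* Nothing in the documents links concentration to infusion reactions. Section 1.1.3 places these reactions generally within 30 to 120 minutes of beginning the first infusion, which the rapid option excludes. The only toxicity that Section 9.4 names under safety and feasibility is grade 3-4 haematological.

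**Conclusion.** The contradiction is real and confined to one place: the second portion of the optional rapid schedule, against item 4(d). It exceeds the stated maximum by a factor of 1.70 to 2.60 if 250 ml is the final volume, or about 1.45 to 2.06 if the drug is added to 250 ml of saline. It does so for all seven tabulated doses. As written it touches up to three infusions per patient, the second to fourth, where a site uses the option.

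The result assumes 375 mg/m², the tabulated body surface areas and, for reading B, the stated vial strength. It is an inconsistency between two instructions rather than a miscalculated figure, and no endpoint, analysis or sample size depends on it. It should still be corrected, because following the text as printed breaks the protocol's own limit.

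**What to change.** The sponsor's clinical and pharmacy team should reconcile three places in Attachment 4: item 4(d), the escalation rule in the administration text, and the rapid-infusion block. After the change, concentration, volume and rate steps should agree, or any intended exception should be stated. The revision should say whether 250 ml is the final volume or the saline before the drug is added, and should make clear that the footnote equating ml/h with mg/h holds only at 1 mg/ml. Which values are right is for that team to decide; none is proposed here.

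The cost is a few lines of wording in one attachment. The contradiction does not itself call for a new CRF field or any change to the analysis.
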